12.9 Investigator's Assessment of Adverse Events

The determination of seriousness, severity, and causality will be made by an on-site investigator who is qualified (licensed) to diagnose adverse event information, provide a medical evaluation of adverse events, and classify adverse events based upon medical judgment. This includes but is not limited to physicians, physician assistants, and nurse practitioners.

Laboratory abnormalities will be reported as AEs if there is a 2 times standard deviation increase above baseline.

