5.2.7 Enrollment, Screen Failures, and Study Completion

Patients are considered enrolled from time consented to participate until designated as a screen failure or have either been discontinued from the study or completed it. A screen failure is a patient who signed informed consent, but then was determined to be ineligible or withdraws from the study. Subjects are considered to have completed the study when they are followed through day 60 or have had an adverse event or death occurred prior to day 60.

Day -1 to 0 Baseline:

- A. Subject informed consent (obtained before performing study related activities)
- B. Baseline Evaluation at screening.
 1. Demographics (Age, sex ethnicity, race)
 2. Medical history (timing of exposure to COVID-19 source patient, acute and chronic medical condition, medications, allergies.) Any medical condition arising after consent should be recorded as AE.
 3. COVID-19 symptom screen (fevers, cough, shortness of breath, diarrhea, anosmia), onset of symptoms, source of contagion
 4. Vital signs

5. COVID-19 testing (RT-PCR) from nasopharyngeal, throat, tracheal aspirate or bronchoalveolar lavage and stool (optional) samples
6. Blood typing, CBC with differential, comprehensive metabolic panel
7. Serological testing: anti-SARS CoV-2 titers
8. Immune testing samples
9. Urine or serum pregnancy test for females of childbearing potential. Results from laboratory tests obtained up to 7 days before enrollment may be used for the pregnancy test.
10. Determination of eligibility as per inclusion/exclusion criteria, age, consent, positive for COVID-19, respiratory symptoms within 72 hours of admission

DAY 0 Baseline and Infusion:

1. Study Plasma Administration: 1-2 units of plasma will be transfused over 1-2 days. Time at start and end of infusion will be recorded and vital signs will be measured immediately prior to infusion, 10-20 minutes after start of infusion, at completion of infusion and 30-60 minutes after the end of the infusion
2. COVID-19 symptom screen (fevers, cough, shortness of breath)
3. Assessment of clinical status (8-point ordinal scale)
4. New medical conditions, concomitant medication, AE evaluation
5. Physical examination
6. COVID-19 testing (RT-PCR) from nasopharyngeal, throat or stool (optional) samples
7. Blood typing, CBC with differential, comprehensive metabolic panel, C-reactive protein
8. Serological testing: anti-SARS CoV-2 titers

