9. Blood for Immune evaluations of cellular and humoral immunity (4 green tops, 30-40 milliliters).

Day 1-7 (or for duration of hospitalization)

1. Vital signs daily (including supplemental oxygen requirements)
2. COVID-19 symptom screen (fevers, cough, shortness of breath)
3. Assessment of clinical status (8-point ordinal scale)
4. New medical conditions, AE evaluation
5. Physical examination
6. CBC with differential, comprehensive metabolic panel, CRP daily

Days 0, 4 (\pm 1 day), 7 (\pm 2 day), 14 (\pm 3 days), 21 (\pm 3 days), and 28 (\pm 3 days):

1. SARS-CoV-2 PCR from oropharyngeal or nasopharyngeal swabs: Day 0, 4, 7, 14, 21 and at any time when there is clinical suspicion for COVID-19.
2. Serum or plasma antibody titer to SARS-CoV-2: Day 0, 7, 14, and 28
3. Blood for immune evaluations of cellular and humoral immunity before CIP infusion (day 0) and 7, 14, and 28 days after CIP infusion (4 green tops, 30-40 milliliters). Immune testing may be done at any time if the PI determines there is a need to evaluate acute immune responses (cytokines/chemokines levels).

Key issues to consider follow up by phone, alive, at home, in hospital (ICU or not), on supplemental O₂ or not, back to work, fully and partially

- COVID-19 symptom screen (fevers, cough, shortness of breath)
- Assessment of clinical status (8-point ordinal scale)
- New medical conditions, AE evaluation

Day 60 (\pm 7 days):

1. COVID-19 symptom screen (fevers, cough, shortness of breath)

2. Assessment of clinical status (8-point ordinal scale)
3. New medical conditions, AE evaluation

One year (\pm 1 month) - *optional*

- 1. Serum or plasma antibody titer to SARS-CoV-2**
- 2. Blood for immune evaluations of cellular and humoral immunity**
- 3. CBC with differential, Comprehensive metabolic panel, PT/INR, PTT, Quantitative immunoglobulins**
- 4. Interval medical history**
- 5. Subject questionnaires regarding health status**

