5.6 Known potential risks

5.6.1 Antibody-Mediated Enhancement of Infection (ADE)

The theoretical risk involves the phenomenon of antibody-mediated enhancement of infection (ADE). ADE can occur for several viral diseases and involves an enhancement of disease in the presence of certain antibodies. For coronaviruses, several mechanisms for ADE have been described and there is the theoretical concern that antibodies to one type of coronavirus could enhance infection to another viral strain¹¹. It may be possible to predict the risk of ADE of SARS-CoV-2 experimentally, as proposed for MERS. Since the proposed use of convalescent plasma in the COVID-19 epidemic would rely on preparations with high titers of antibody against the same virus, SARS2-CoV-2, ADE may be unlikely. The available evidence from the use of convalescent plasma in patients with SARS1 and MERS¹² and anecdotal evidence of its use in patients with

COVID-19¹³, suggest it is safe. Nevertheless, caution and vigilance will be required in for any evidence of enhanced infection. Alterations in serum potassium and calcium levels can occur with these patients.

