9.3 Analysis of AE data

Analysis of AE data will primarily be descriptive based on MedDRA coding of events. The proportion of subjects experiencing an SAE and the proportion experiencing a Grade 3 or higher will be recorded. AE will be compared to published data.

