10.7 Laboratory and Clinical Data Review

The Investigator, or designee, must review all laboratory values and report any clinically significant change compared to the baseline sample as an AE. When reporting such AEs the Investigator will use the appropriate clinical term, rather than the laboratory test result (e.g. anemia versus low hemoglobin).

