12.0 ADVERSE EVENTS AND SAFETY EVALUATION

Adverse events will be evaluated and scored using Common Terminology Criteria for Adverse Events version 5.0 (CTCAE v5.0). ctep.cancer.gov/.../CTCAE_v5_Quick_Reference_5x7.pdf

1. Safety Evaluations will assess for the safety of high titer anti-SARS-CoV-2 plasma
2. Clinical evaluations: Vital signs and symptom screen on days 0-7, 14 and symptom screens on days 28, and 60.
3. Safety Evaluations will assess for the safety of high titer anti-SARS-CoV-2 plasma
4. Clinical evaluations: Vital signs and symptom screen on days 0-7, 14 and symptom screens on days 28, and 60.
5. Laboratory evaluations consistent with ongoing medical care may include radiographic imaging modalities such as chest x-rays and chest CT.
6. Safety laboratory tests (ABO typing, pregnancy testing, CBC, CRP, and comprehensive metabolic panel) will be performed at the local CLIA-certified clinical laboratory on days 0-7 and 14.

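### The laboratory AE trigger in section 12.9 counts only increases, does not say which SD applies, and is not reconciled with section 10.7, so the any-grade laboratory AE list depends on which rule and which SD are used

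*Combined protocol and SAP*

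**What the plan says.** Two sections of the combined protocol and SAP decide when a laboratory value becomes an adverse event.

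- Section 12.9: "Laboratory abnormalities will be reported as AEs if there is a 2 times standard deviation increase above baseline".
- Section 10.7: the investigator or designee "must review all laboratory values and report any clinically significant change compared to the baseline sample as an AE". For such events, "the Investigator will use the appropriate clinical term, rather than the laboratory test result (e.g. anemia versus low hemoglobin"; the example is a decrease.

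Other sections bear on how the two are read.

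- Section 5.6.1 names an expected laboratory risk without restricting its direction: "Alterations in serum potassium and calcium levels can occur with these patients". Section 5.1 lists electrolyte disturbances among the events to be documented.
- Section 12.1 allows an abnormal laboratory finding to be an AE.
- Section 12.0: "Adverse events will be evaluated and scored using Common Terminology Criteria for Adverse Events version 5.0 (CTCAE v5.0". Section 12.10.1 then gives a separate five-level severity scale, worded in terms of discomfort and intervention.
- Section 9.3 plans a descriptive AE analysis: "The proportion of subjects experiencing an SAE and the proportion experiencing a Grade 3 or higher will be recorded". It also says that AEs will be compared with published data.
- Stopping criterion 4 in section 15.0 needs two subjects with persistent Grade 3 or higher toxicity in the same laboratory parameter, associated with the product.

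**The concern.** A trigger that decides what enters the AE list should give the same list whoever applies it. The one in section 12.9 does not, for three reasons.

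1. It is one-directional. A fall in calcium, potassium, platelets or lymphocytes can never meet it, however large.
2. Its unit is missing. No section says which SD is to be doubled.
3. It stands beside a different rule in section 10.7, and neither refers to the other. Section 12.9 calls for reporting on a statistical threshold whatever the clinical relevance. Section 10.7 calls for reporting on clinical relevance whatever the threshold.

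What is at stake is the any-grade laboratory AE list: whether it can be reproduced, and whether setting it against published data means anything. Safety is a secondary objective, and with 29 treated patients a few events classified differently visibly move a proportion.

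**Working it through.** The plan gives no SD, no expected laboratory AE rate and no calculation for this rule, so there is no figure to reproduce. The check has two parts.

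**The text side by side**

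| Feature | Section 12.9 | Section 10.7 |
|---|---|---|
| Direction | Increase only | Any change; the example is a fall |
| Threshold | 2 SD, source not stated | Clinical significance |
| Reference point | Baseline | The baseline sample |
| Link to the other rule | None | None |
| Link to a grading scale | None | None |

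The number of baseline values is also unsettled. Table 1 marks CBC and CMP once before infusion. Section 5.2.7 lists them under Day -1 to 0 and again under Day 0 ("Blood typing, CBC with differential, comprehensive metabolic panel, C-reactive protein"). A sample SD divides by n − 1. With one value that is 0, so a patient's own SD is undefined; with two values it has 1 degree of freedom.

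**How much the choice of SD matters**

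Input from the documents: seven daily draws. Section 5.2.7 lists, for days 1–7, "CBC with differential, comprehensive metabolic panel, CRP daily". Section 12.8 documents AEs for seven days from first administration.

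Assumptions that are not in the documents: normal values, no true change, draws independent around the patient's own level, and a patient who stays in hospital for all seven draws. Write σw for the within-patient SD and ρ for the within-patient correlation, so that σw = cohort SD × √(1 − ρ).

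*(a) Cohort SD, one baseline value.* A follow-up minus baseline difference has SD σw√2, so the chance of a flag per draw is P(Z > 2/√(2(1 − ρ))).
- ρ = 0.3: 2/√1.4 = 1.69
- ρ = 0.5: 2/√1.0 = 2.00
- ρ = 0.7: 2/√0.6 = 2.58
- ρ = 0.9: 2/√0.2 = 4.47

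*(b) Known within-patient SD, one baseline value.* P(Z > 2/√2) = P(Z > 1.41).

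*(c) Patient's own SD from two pre-infusion values, baseline taken as their mean.* The difference has variance 1 + 1/2 = 1.5 in units of σw², and the SD has 1 degree of freedom. The chance is P(t with 1 df > 2/√1.5) = P(t > 1.63).

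For at least one flag in seven draws the shared baseline must be averaged over. In (a) and (b) the chance is 1 − E[Φ(B + k)^7], with B standard normal and k = 2 × SD/σw. In (c) it is 1 − E[Φ(M + 2S)^7], with M normal with variance 1/2 and S the absolute value of an independent standard normal.

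| Reading of the SD | Per draw | At least once in 7 draws |
|---|---|---|
| (a) Cohort, ρ = 0.3 | 4.5% | 18.8% |
| (a) Cohort, ρ = 0.5 | 2.3% | 10.6% |
| (a) Cohort, ρ = 0.7 | 0.5% | 2.7% |
| (a) Cohort, ρ = 0.9 | about 0% | about 0% |
| (b) Within-patient, known | 7.9% | about 29% |
| (c) Patient's own, two values | 17.5% | 47.0% |

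These are rises only. Chance falls of the same size are equally frequent, and section 12.9 flags none of them. Counting both directions about doubles the per-draw rate, for example from 7.9% to 15.7% in (b).

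An assay SD is not in the table because the documents give no figure for it. Assay variation is part of within-patient variation, so its SD cannot exceed σw, and the rate under that reading would be at least that of (b).

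**The case against.** The strongest reply is that section 12.9 says abnormalities are reported if the threshold is met, not only if. Read as one sufficient trigger, it can coexist with section 10.7, which covers falls. Sections 12.1 and 5.1 point the same way. This stands: a reader might infer that falls are lost to the trial, and the protocol as a whole does not support that. What remains is that section 12.9 itself is one-directional, and nothing tells staff that it supplements section 10.7 and does not define the laboratory AE.

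Three other stronger readings are tempting.

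- *That the SD cannot exist because each patient has one baseline value.* Section 12.9 does not say that the SD is the patient's own. A cohort, assay or reference-range SD could be computed, and section 5.2.7 lists two pre-infusion draws. The supportable statement is that the SD is not specified.
- *That the Grade 3 or 4 endpoint and stopping criterion 4 turn on the 2-SD rule.* Both rest on grade. A chance rise of 2 SD is not thereby Grade 3, and a severe fall would ordinarily be clinically significant under section 10.7. The Safety Review Committee in section 16.3 also sees clinical laboratory data.
- *That each patient would have about 6 to 14 spurious AEs.* This comes from 7.9% × 7 draws × an assumed 10 to 25 analytes = 5.5 to 13.8. It uses one SD reading and counts repeated flags from a shared baseline as separate events, whereas section 12.8 follows an AE to resolution. Under that same reading, 29% × 10 to 25 gives about 3 to 7 distinct analytes. The documents support neither the analyte count nor the SD reading, so neither total should be cited.

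It is also fair to say that daily testing stops at discharge, and that section 12.9 speaks of abnormalities while the calculation counts any stable value, including those within the normal range. Both lower the rates in practice.

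**Conclusion.** The point holds as a defect in a stated rule. Section 12.9 counts only increases, leaves its SD unspecified, and is not reconciled with section 10.7. Two people applying the plan in good faith could produce different any-grade laboratory AE lists, and a comparison of that list with published data would partly reflect which rule was used.

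On the readings calculated, the chance of flagging one unchanged analyte over seven daily draws runs from about 0% to 47%. That range rests on assumed normality, independent draws, a correlation of 0.3 to 0.9 and a full seven days in hospital. It shows how sensitive the rule is to the missing definition; it does not predict this trial's AE count.

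A reader might conclude that laboratory safety cannot be interpreted at all. The documents do not support that. The planned SAE and Grade 3 or higher proportions and stopping criterion 4 do not use the 2-SD threshold. Their only exposure is that an abnormality not recorded as an AE might never be graded.

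**What to change.** Delete the 2-SD sentence from section 12.9 and put one rule in both 10.7 and 12.9. Report as an AE any laboratory change from the pre-infusion baseline, in either direction, that worsens by at least one CTCAE v5.0 grade or that the investigator judges clinically significant.

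Two additions make it workable.

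- State that laboratory values are graded by CTCAE v5.0, which section 12.0 already adopts, and not by the section 12.10.1 scale. The latter has no laboratory thresholds, so a one-grade worsening could not be applied to a laboratory value under it. An analyte without a CTCAE grade falls under the clinical-significance limb.
- Say which pre-infusion sample is the baseline, and align section 5.2.7 with Table 1 on this.

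The cost is protocol wording and a little more grading work. No new samples, visits or patients are needed.

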12.10 Assessment of Seriousness

1. Event seriousness will be determined according to the protocol definition of an SAE

2. Assessment of Severity

12.10.1 Event severity

Will be assigned according to the scale below:

- 1 = Mild: Transient or mild discomfort (<48 hours); no medical intervention/therapy required.)
- 2 = Moderate: Some worsening of symptoms but no or minimal medical intervention/therapy required)
- 3 = Severe: Escalation of medical intervention/therapy required
- 4 = Life-threatening: Marked escalation of medical intervention/therapy required.
- 5= Death

12.11 Assessment of Association

The association assessment categories that will be used for this study are:

- Associated – The event is temporally related to the administration of the study product and no other etiology explains the event.
- Not Associated – The event is temporally independent of the study product and/or the event appears to be explained by another etiology.

The investigator must provide an assessment of association or relationship of AEs to the study product based on:

- Temporal relationship of the event to the administration of study product;
- Whether an alternative etiology has been identified;
- Biological plausibility;
- Existing therapy and/or concomitant medications

13.0 REPORTING ADVERSE REACTIONS

- **Investigators are required to notify the FDA and IRB** of all serious and unexpected adverse drug reactions.
- **All reactions in a 'reportable' category must be reported** unless it is documented in the medical record chart that treatment is definitely **not** responsible for the toxicity.
- **Serious and unexpected adverse reactions** will be reported to the following sources within the stated time frame:
- **All participating investigators:** Written IND safety report within 10 working days.
- **IRB:** Notify IRB in written report within 10 working days.
- **FDA:** Written IND safety report within 10 calendar days. Report by telephone within three working days. Include reports in annual report.

13.1 Procedure for calling the FDA:

The sponsor or designated PI or research nurse will call for ADRs.

The principal investigator or his designee will email or call for regulatory/protocol issues.

The medical reviewer for the FDA is:

[Will be identified by FDA]

Center for Biologics Evaluation and Research

Food and Drug Administration

Division of Biological Investigational New Drugs

[name]

Rockville, MD 20852

Document as completely as possible, and send copies to:

Patient's chart

Protocol binder
UVA Institutional Review Board
FDA correspondence binder
[name], DSc, Director of Cellular therapy and Director cGMP Facility
Co-investigators for the protocol

14.0 SAFETY OVERSIGHT

14.1 Monitoring Plan

1. All AE and SAW will be reviewed by protocol team in real time.
2. A medical monitor will be appointed by the sponsor for safety oversight of the clinical study.
3. A data safety monitoring board (DSMB) composed of independent experts without conflict of interests. The Board will review the study before initiation and every 3 months thereafter. The Board will review study data to evaluate the safety, efficacy, study progress, and conduct of the study
4. An Independent Safety Monitor (ISM) will be appointed. The ISM is a physician with expertise in infectious diseases and whose primary responsibility is to provide timely independent safety monitoring. An ISM is in close proximity to the study site and has the authority to readily access study participant records. The ISM reviews any SAE that occurs at the study site in real time and provides a written assessment.

14.2 Study monitoring

1. As per ICH-GCP 5.18 and FDA 21 CFR 312.50, clinical protocols are required to be adequately monitored by the study sponsor. Monitors will verify that
 - a. There is documentation of the informed consent process and signed informed consent documents for each subject
 - b. There is compliance with recording requirements for data points
 - c. All SAEs are reported as required
 - d. Individual subjects' study records and source documents align
 - e. Investigators are in compliance with the protocol.
 - f. Regulatory requirements as per Office for Human Research Protections-OHRP), FDA, and applicable guidelines (ICH-GCP) are being followed.

15.0 STOPPING RULES

The study enrollment and dosing will be stopped and an ad hoc review will be performed if any of the specific following events occur or, if in the judgment of the study physician, subject safety is at risk of being compromised:

1. Death within one hour of plasma infusion
2. Occurrence of a life-threatening allergic/hypersensitivity reaction (anaphylaxis), manifested by bronchospasm with or without urticaria or angioedema requiring hemodynamic support with pressor medications or mechanical ventilation, TRALI, or TACO
3. One subject with a grade 4 or persistent grade 3 (≥ 72 hours) associated with study product.
4. Two subjects with persistent Grade 3 (≥ 72 hours) or higher lab toxicity for the same parameter associated with study product.
5. An overall pattern of symptomatic, clinical, or laboratory events that the medical monitor, ISM, or SMC consider associated with study product and that may appear minor in terms of individual events but that collectively may represent a serious potential concern for safety.
6. Any other event(s) which is considered to be a serious adverse event in the good clinical judgment of the attending physician team. This will be appropriately documented.

Upon completion of this review and receipt of the advice of the ISM or SMC, DMID will determine if study entry or study dosing should be interrupted or if study entry and study dosing may continue according to the protocol.

15.1 Stopping Rules

Infusion of study drug will be halted if any of the following manifestations of anaphylaxis develop and will not be restarted:

- Skin or mucous membrane manifestations: hives, pruritus, flushing, swollen lips, tongue or uvula
- Respiratory compromise: dyspnea, wheezing, stridor, hypoxemia
- A decrease in systolic blood pressure to < 90 mmHg or >30% decrease from baseline or a diastolic drop of >30% from baseline.
- Tachycardia with an increase in resting heart rate to > 130bpm; or bradycardia <40 that is associated with dizziness, nausea or feeling faint.
- Any other symptom or sign which in the good clinical judgment of the study clinician or supervising physician warrants halting the infusion. For example, the rapid onset of gastrointestinal symptoms, such as nausea, vomiting, diarrhea, and cramps, for instance, may be manifestations of anaphylaxis and may warrant an immediate halt prior to meeting full SAE criteria

